10.10 APPENDIX 10: DEFINITION OF ANAPHYLAXIS

“Anaphylaxis is a serious allergic reaction that is rapid in onset and may cause death (39)”.

Clinical criteria for diagnosing anaphylaxis

Anaphylaxis is highly likely when any one of the following 3 criteria are fulfilled:

1. Acute onset of an illness (minutes to several hours) with involvement of the skin, mucosal tissue, or both (eg, generalized hives, pruritus or flushing, swollen lips-tongue-uvula)
AND AT LEAST ONE OF THE FOLLOWING
 - a. Respiratory compromise (eg, dyspnea, wheeze-bronchospasm, stridor, reduced PEF, hypoxemia)
 - b. Reduced BP or associated symptoms of end-organ dysfunction (eg, hypotonia [collapse], syncope, incontinence)
2. Two or more of the following that occur rapidly after exposure to *a likely allergen for that patient* (minutes to several hours):
 - a. Involvement of the skin-mucosal tissue (eg, generalized hives, itch-flush, swollen lips-tongue-uvula)
 - b. Respiratory compromise (eg, dyspnea, wheeze-bronchospasm, stridor, reduced PEF, hypoxemia)
 - c. Reduced BP or associated symptoms (eg, hypotonia [collapse], syncope, incontinence)
 - d. Persistent gastrointestinal symptoms (eg, crampy abdominal pain, vomiting)
3. Reduced BP after exposure to *known allergen for that patient* (minutes to several hours):
 - a. Infants and children: low systolic BP (age specific) or greater than 30% decrease in systolic BP*
 - b. Adults: systolic BP of less than 90 mm Hg or greater than 30% decrease from that person's baseline

PEF, Peak expiratory flow; *BP*, blood pressure.

*Low systolic blood pressure for children is defined as less than 70 mm Hg from 1 month to 1 year, less than $(70 \text{ mm Hg} + [2 \times \text{age}])$ from 1 to 10 years, and less than 90 mm Hg from 11 to 17 years.

10.11 APPENDIX 11: LIST OF OPPORTUNISTIC INFECTIONS

- Aspergillosis
- Blastomyces dermatitidis (endemic in the south-eastern and south-central states US, along Mississippi and Ohio Rivers)
- Candidiasis - only systemic or extensive mucosal or cutaneous candidiasis
- Coccidioides immitis (endemic south-western US and Central and South America)
- Cryptococcus
- Cytomegalovirus
- Herpes Simplex (disseminated)
- Herpes Zoster (disseminated; ophthalmic; involvement of 2 or more dermatomes)
- Histoplasmosis (pulmonary or disseminated; most common tropical areas Tennessee-Ohio-Mississippi river basins)
- Listeriosis
- Mycobacterium TB
- Mycobacterium avium
- Non-TB mycobacteria
- Pneumocystis pneumonia

This list is indicative and not exhaustive.

10.12 APPENDIX 12: LIST OF PROHIBITED LIVE ATTENUATED VACCINES

- Bacillus Calmette-Guérin (BCG) anti-TB vaccine
- Chickenpox (Varicella)
- Intranasal influenza (FluMist-Influenza); inactive influenza vaccine delivered by injection is permitted
- Measles (Rubeola)
- Measles-mumps-rubella combination
- Measles-mumps-rubella-varicella combination
- Mumps
- Oral polio (Sabin)
- Oral typhoid
- Rotavirus
- Rubella
- Smallpox (Vaccinia)
- Varicella Zoster (shingles)
- Yellow fever

This list is indicative and not exhaustive.

10.13 APPENDIX 13: ESTIMANDS FOR MAIN ENDPOINTS

Table 11 - Summary of primary estimand for main endpoints in ColdU study

Endpoint Category (estimand)	Estimands				Population-level summary
	Endpoint	Population	Intercurrent event(s) strategy and missing data handling		
Primary objective: To demonstrate the efficacy of dupilumab in adult and adolescent participants with primary acquired chronic inducible ColdU who remain symptomatic despite the use of an H1-antihistamine					
Primary endpoint (treatment policy/composite estimand)	Proportion of participants with negative ice cube provocation test at Week 24	ITT	Discontinuation of the study intervention before Week 24 (but not taking highly influential prohibited medications and/or highly influential rescue medications prior to Week 24): Off-study intervention data up to Week 24 will be included in the analysis (treatment policy strategy). Taking highly influential prohibited medications and/or highly influential rescue medications prior to Week 24: Participants will be considered as having positive ice cube provocation tests at Week 24 (composite strategy). Having missing data at Week 24: Participants will be considered as having positive ice cube provocation tests at Week 24.	CMH test stratified by region (combined countries) and background H1-antihistamine regular/daily use (Yes/No). The comparison of the proportions of treatment response between dupilumab and placebo will be derived, and the corresponding odd ratios and the 95% CI will be reported.	
Secondary objective: To demonstrate the efficacy of dupilumab on primary acquired chronic inducible ColdU local signs and symptoms					
Secondary endpoint (treatment policy/composite estimand)	Change from baseline in local wheal intensity at the provocation site at Week 24 using the wheal intensity Likert scale ranging from 0 to 5 (clinician evaluation)	ITT	The intercurrent events will be handled as below: 
Discontinuation of the study intervention before Week 24 (but not taking highly influential prohibited medications and/or highly influential rescue medications prior to Week 24): Off-study intervention data up to Week 24 will be included in the analysis (treatment policy strategy)	ANCOVA model with treatment group, baseline value, region, and background H1-antihistamine regular/daily use (Yes/No) as covariates will be used. Statistical inference obtained from all imputed data by ANCOVA model will be combined using Rubin's rule.	

Endpoint Category (estimand)	Estimands				Population-level summary
	Endpoint	Population	Intercurrent event(s) strategy and missing data handling		
	Change from baseline in the proportion of cold urticaria sign and symptom free days at Week 24 on cold exposure days as measured by ColdUAS	ITT	
 • Taking highly influential prohibited medications and/or highly influential rescue medications prior to Week 24: data will be set to missing values after the medication usage, and the WOOF approach (worst postbaseline observation for the participant will be carried forward) will be used to impute missing endpoint value (for participants whose postbaseline values are all missing, the participant's baseline value will be used to impute the missing endpoint value) (composite strategy) 
Missing data handling:
 
 • For participants who discontinue study intervention due to lack of efficacy, all data collected after discontinuation will be used in the analysis, and a WOOF approach will be used to impute missing Week 24 value if needed. For participants who discontinue study intervention not due to lack of efficacy, a multiple imputation approach will be used to impute missing Week 24 value, and this multiple imputation will use all participants excluding participants who have taken the highly influential prohibited medications and/or highly influential rescue medications on or before Week 24 and excluding patients who discontinue due to lack of efficacy on or before Week 24. 	Descriptive statistics including number of participants, mean, standard error, and least squares (LS) mean changes (and standard error) score will be provided. In addition, difference of the dupilumab group against placebo in LS means and the corresponding 95% CI will be provided along with the p-values.	

Abbreviations: ANCOVA = Analysis of covariance, CI = confidence interval, CMH = Cochran-Mantel-Haenszel, ColdU = cold urticaria, ITT= Intent-to-treat.

Additional secondary objectives/endpoints are not included in this table but would be handled with a similar strategy as the endpoint type (ie, continuous, proportion) at other weeks.

10.14 APPENDIX 14: ABBREVIATIONS

ACU:	acquired cold urticaria
ACUSI:	Acquired Cold Urticaria Severity Index
AD:	atopic dermatitis
ADA:	antidrug antibody
ADR:	adverse drug reaction
AEs:	adverse event(s)
AESI:	adverse event of special interest
ALT:	alanine aminotransferase
ANCOVA:	Analysis of covariance
CDLQI:	Children's Dermatology Life Quality Index
CFR:	Code of Federal Regulations
CholU:	cholinergic urticaria
CI:	confidence interval
CIndU:	Chronic Inducible Urticaria
ColdU:	cold urticaria
ColdUAS:	Cold Urticaria Activity Score
ColdU-QoL:	Cold Urticaria Quality of Life
COPD:	chronic obstructive pulmonary disease
COVID-19:	Coronavirus Disease 2019
CRF:	case report form
CRSwNP:	chronic rhinosinusitis with nasal polyposis
CSICF:	Core Study Informed Consent Form
CSR:	clinical study report
CSTT:	cold-simulation time test
CSU:	Chronic Spontaneous Urticaria
DLQI:	Dermatology Life Quality Index
DNA:	Deoxyribonucleic acid
DPU:	delayed pressure urticaria
DTP:	direct to patient
ECG:	electrocardiogram
eCRF:	electronic case report form
ELISA:	enzyme-linked immunosorbent assay
EoE:	eosinophilic esophagitis
EOT:	end of treatment
EQ-5D:	EuroQol-5 dimensions
EQ-5D-5L:	5-level EuroQol 5 dimensional questionnaire
EQ-VAS:	EuroQol visual analogue scale
EU:	European Union
Fc ϵ RI:	Fc epsilon receptor
GCP:	Good Clinical Practice
GDPR:	General Data Protection Regulation
HBc Ab:	hepatitis B core antibody

HBs Ag:	hepatitis B virus surface antigen
HBV:	hepatitis B virus
HCV:	hepatitis C virus
HCV Ab:	Hepatitis C antibody
HIV:	human immunodeficiency virus
HRQoL:	health-related quality of life
HRT:	hormone replacement therapy
IB:	Investigator's brochure
ICF:	informed consent form
ICH:	International Council of Harmonisation
IEC:	Institutional Ethics Committee
IgE:	immunoglobulin E
IL:	Interleukin
IL-4R α :	interleukin-4 receptor alpha subunit
IMP:	investigational medicinal product
IRB:	Institutional Review Boards
IRT:	interactive response technology
ITT:	Intent-to-treat
IVIG:	intravenous immunoglobulin
IVRS:	interactive voice response system
IWRS:	interactive web response system
LS:	least squares
LTE4:	leukotriene E4
LTRAs:	Leukotriene receptor antagonists
mAb:	monoclonal antibody
MID:	minimal important difference
NIMP:	noninvestigational medicinal product
NRS:	Numerical Rating Scale
OCS:	oral corticosteroids
PD:	pharmacodynamics
PGDM:	prostaglandin D2 metabolite
PGIC:	Patient Global Impression of Change
PGIS:	Patient Global Impression of Severity
PK:	pharmacokinetics
PN:	prurigo nodularis
PRO:	patient-reported outcome
q2w:	every 2 weeks
qd:	once per day
QoL:	Quality of Life
RNA:	ribonucleic acid
SAE:	serious adverse event
SAP:	statistical analysis plan
SC:	subcutaneous
SCS:	systemic corticosteroids
SoA:	schedule of activities
SUSAR:	suspected unexpected serious adverse reactions

TB:	tuberculosis
TEAE:	treatment-emergent adverse event
Th2:	T helper 2
UCT:	urticaria control test
ULN:	upper limit of normal
US:	United States
WOCBP:	woman of childbearing potential
WOCF:	worst observation carried forward

10.15 APPENDIX 15: PROTOCOL AMENDMENT HISTORY

The Protocol Amendment Summary of Changes Table for the current amendment is located directly before the table of contents (TOC).

1 INTRODUCTION

1.1 STUDY DESIGN

The EFC16720 study is a 24-week, randomized, double-blind, placebo-controlled, parallel-group, multi-center study to evaluate the use of dupilumab in adults and adolescents (≥ 12 to < 18 years old) with primary acquired chronic inducible cold urticaria (ColdU) who remain symptomatic despite the use of H1-antihistamine treatment. The study is designed to test the hypothesis that dupilumab will increase the proportion of participants with a negative ice cube provocation test at Week 24 compared with placebo. A negative ice cube provocation test is defined as the absence of a confluent hive/wheal at the entire skin site of exposure after an ice cube provocation test.

The study consists of 3 periods:

- Screening period (2 to 4 weeks).
- Randomized IMP treatment period (24 weeks).
- Post IMP treatment period (12 weeks).

Chronic inducible ColdU signs and symptoms will be evaluated after the ice cube provocation test, by the Investigator (hives/wheals intensity) and participant (itch severity, skin pain, skin sensation). In addition, chronic inducible ColdU disease activity will be assessed daily by the participant using ColdUAS questionnaire in an e-diary where the participant will report his/her skin reactions (wheals and swelling), skin sensations (itching, burning, pain or feeling hot), if they have been in contact with cold temperatures that usually cause skin reactions, if they have avoided trigger exposure, and overall symptoms severity. The study will also assess the effect of dupilumab on urticaria control, participants' HRQoL and overall health status, proportion of patients with cold urticaria requiring emergency medical care visit or treatment with epinephrine and on reduction of rescue therapy.

The total anticipated number of participants randomized in the study is 78. This corresponds to approximately 39 participants who will be randomly assigned to each intervention arm:

- Dupilumab: 300 mg every q2w for adults; 200 mg q2w for adolescents ≥ 30 kg and < 60 kg at baseline or 300 mg q2w for adolescents ≥ 60 kg at baseline.
- Matched placebo.

At least 4 participants randomized in the study will be adolescents (≥ 12 to < 18 years old) who will be recruited in a few selected sites in selected countries. Randomization will be stratified by age (adolescent versus adult) and within adult group by country and background H1-antihistamine regular/daily use (Yes/No).

The number of participants using H1-antihistamine as needed prior to study entry should be at least [REDACTED]

During the study, participants should continue their established standard of care background therapy with a long acting non-sedating H1-antihistamine, at up to 4-fold (2-fold in Japan) the approved dose for Chronic Spontaneous Urticaria (CSU).

- Participants who used H1-antihistamine regularly/daily prior to study entry should continue to take it daily. Note: regular/daily use of H1-antihistamine prior to study entry is defined as H1-antihistamine intake for at least 4 days per week for at least 1 month prior to screening visit (Visit 1).
- Participants who took H1-antihistamine as needed prior to study entry should limit the use to short-term.

The H1-antihistamine dose used during the study should be the same dose the participants took to prevent ColdU symptoms prior to study entry (“prescreening dose”). However, if participants experience a flare rescue therapy may be initiated.

If participants are on a dose higher than 4-fold (2-fold in Japan) the approved CSU dose at the screening visit (Visit 1), the investigator can adjust the participant’s dose within the stipulated range at the screening visit (Visit 1).

All participants will be allowed to take study-defined H1-antihistamine as rescue therapy as long as they do not exceed 4-fold (2-fold in Japan) the approved CSU dose during screening, treatment, and follow-up periods. If symptoms are still uncontrolled after increase of H1-antihistamine to the maximum allowed dose, or if the participant is already on the 4-fold (2-fold in Japan) approved dose of H1-antihistamine, participants can switch to another antihistamine up to 4-fold (2-fold in Japan) the approved dose for CSU or a short course of oral corticosteroids (OCS) is allowed during the treatment and follow-up periods. However, for the purpose of the primary analysis, data collected after OCS use will be set to missing and the worst post-baseline value before OCS will be used to impute the data.

1.2 OBJECTIVE AND ENDPOINTS

Table 1 - Objectives and endpoints

Objectives	Endpoints
Primary	

• To demonstrate the efficacy of dupilumab in adult and adolescent participants with primary acquired chronic inducible cold urticaria (ColdU) who remain symptomatic despite the use of an H1-antihistamine	
• Proportion of participants with negative ice cube provocation test [*] at Week 24 compared with placebo <small>*Negative ice cube provocation test is defined as the absence of a confluent hives/wheel at the entire skin site of exposure after ice cube provocation test ^a</small>
Secondary	

• To demonstrate the efficacy of dupilumab on primary acquired chronic inducible ColdU disease control	
• Change from baseline in urticaria control test (UCT 4-item) at Week 24 compared with placebo• Proportion of well-controlled participants (UCT \geq12) at Week 24 compared with placebo

Objectives	Endpoints

• To demonstrate the efficacy of dupilumab on primary acquired chronic inducible ColdU local signs and symptoms (hives/wheals, itch, burning sensation and pain) after provocation test• To demonstrate the efficacy of dupilumab on primary acquired chronic inducible ColdU disease activity• To demonstrate improvement in health-related quality-of-life and overall disease status and severity• To evaluate the ability of dupilumab in reducing the proportion of participants who require rescue therapy• To evaluate the proportion of participants with cold exposure triggered urticaria• To evaluate safety outcome measures	
• Proportion of participants with an improvement of ≥ 3 in UCT 4-item from baseline to Week 24 compared with placebo.• Change from baseline in local wheal intensity at the provocation site at Week 12 and Week 24 using the wheal intensity Likert scale ranging from 0 to 5 (clinician evaluation) compared with placebo• Change from baseline in local itch severity at the provocation site at Week 12 and Week 24 using the Peak Pruritus Numerical Rating Scale (NRS, score 0 to 10) (patient reported) compared with placebo• Change from baseline in local skin burning sensation at the provocation site at Week 12 and Week 24 using the peak burning sensation NRS (patient reported) compared with placebo• Change from baseline in local pain severity at the provocation site at Week 12 and Week 24 using the peak pain sensation NRS (patient reported) compared with placebo• Proportion of participants with negative ice cube provocation test at Week 12 compared with placebo• Change from baseline in cold urticaria signs and symptoms severity at Week 24 on cold exposure days as measured by ColdUAS, compared with placebo• Change from baseline in the proportion of cold urticaria sign and symptom free days at Week 24 on cold exposure days as measured by ColdUAS, compared with placebo• Change from baseline in health-related quality-of-life (HRQoL) as measured by Dermatology Life Quality Index (DLQI) in participants ≥ 16 years old, and in Children's Dermatology Life Quality Index (CDLQI) in participants ≥ 12 to < 16 years old at Week 24 compared with placebo• Change from baseline in Cold Urticaria Quality of Life (ColdU-QoL) at Week 24 compared with placebo.• Proportion of participants receiving rescue therapy for primary acquired chronic inducible ColdU during the planned treatment period compared with placebo• Proportion of participants with cold exposure triggered urticaria requiring emergency medical care visit or treatment with epinephrine (at provocation test and/or at home)• Percentages of participants experiencing treatment-emergent adverse events (TEAEs) or serious adverse events (SAEs)

Objectives	Endpoints

• To evaluate immunogenicity of dupilumab	
• Incidence of treatment-emergent antidrug antibodies (ADA) against dupilumab over time
Tertiary/exploratory	

Pharmacokinetic (PK)/Pharmacodynamic (PD)

- To evaluate PK of dupilumab
- To evaluate PD effect of dupilumab
- Functional dupilumab concentrations in serum and PK profile
- Total immunoglobulin E over time.

a Provocation test reading time for all endpoints: 15 minutes after the ice cube application start = 5 minutes ice cube application plus 10 minutes after removal of ice cube

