
• To demonstrate improvement in health-related quality-of-life and overall disease status and severity• To evaluate the ability of dupilumab in reducing the proportion of participants who require rescue therapy• To evaluate the proportion of participants with cold exposure triggered urticaria• To evaluate safety outcome measures• To evaluate immunogenicity of dupilumab	
• Change from baseline in health-related quality-of-life (HRQoL) as measured by Dermatology Life Quality Index (DLQI) in participants ≥ 16 years old, and in Children's Dermatology Life Quality Index (CDLQI) in participants ≥ 12 to < 16 years old at Week 24 compared with placebo• Change from baseline in Cold Urticaria Quality of Life (ColdU-QoL) at Week 24 compared with placebo.• Proportion of participants receiving rescue therapy for primary acquired chronic inducible ColdU during the planned treatment period compared with placebo• Proportion of participants with cold exposure triggered urticaria requiring emergency medical care visit or treatment with epinephrine (at provocation test and/or at home)• Percentages of participants experiencing treatment-emergent adverse events (TEAEs) or serious adverse events (SAEs)• Incidence of treatment-emergent antidrug antibodies (ADA) against dupilumab over time

Tertiary/exploratory

Pharmacokinetic (PK)/Pharmacodynamic (PD)

- To evaluate PK of dupilumab
- To evaluate PD effect of dupilumab
- Functional dupilumab concentrations in serum and PK profile
- Total immunoglobulin E over time.

^a Provocation test reading time for all endpoints: 15 minutes after the ice cube application start = 5 minutes ice cube application plus 10 minutes after removal of ice cube

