The clinical picture of a participant at the time of study visits may not be totally representative of the actual current disease status due to symptom fluctuation that is dependent upon the contact with the triggering temperature. Therefore, the participants will rate the disease activity using the ColdUAS questionnaire in an e-diary. On a daily basis, participants will report their skin reactions (wheals and swelling), skin sensations (itching, burning, pain or feeling hot), avoidance behavior and trigger exposure, and overall symptoms severity. Cold Urticaria Activity Score will provide important supportive information on clinical improvement of the participants on a daily basis. Since skin reactions, skin sensations and behavioral avoidance to trigger vary from one day to another, ColdUAS will be assessed on a daily basis.

Participants with primary inducible ColdU are at risk of developing systemic hypersensitivity reactions including anaphylaxis after exposure to cold triggers. Such systemic reactions are mainly described as provoked by aquatic activities (eg, swimming in cold water) when the whole body, or a large proportion of it, was in contact with cold. Systemic hypersensitivity events will be documented via adverse event of special interest (AESI)/serious adverse event (SAE) reporting, and information about corrective treatment will be collected.

To get a complete picture of the disease, it is important to assess disease control over the course of treatment in addition to urticaria symptom assessment. Patients are best positioned to accurately assess this control, as they experience and feel it. They will self-assess their ColdU control using the urticaria control test (UCT), a well-developed and validated instrument in chronic urticaria patients (25).

Lastly, patients with primary acquired chronic inducible ColdU experience substantial HRQoL impairment. Therefore, the DLQI, a dermatology-specific instrument designed to assess HRQoL in adults ≥ 16 years old (26) with dermatologic conditions, and the corresponding Children's Dermatology Life Quality Index (CDLQI) for adolescents aged ≥ 12 years to < 16 years old will be used, in addition to the newly developed disease-specific Cold Urticaria Quality of Life (ColdU-QoL) questionnaire..

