
4.4.2 Supportive secondary endpoint(s)

The change from baseline endpoints:

- Change from baseline in urticaria control test (UCT 4-item) at Week 24
- Change from baseline in local wheal intensity at the provocation site at Week 12 using the wheal intensity Likert scale ranging from 0 to 5 (clinician evaluation)

- Change from baseline in local itch severity at the provocation site at Week 12 and Week 24 using the Peak Pruritus Numerical Rating Scale (NRS, score 0 to 10) (patient reported)
- Change from baseline in local skin burning sensation at the provocation site at Week 12 and Week 24 using the peak burning sensation NRS (patient reported)
- Change from baseline in local pain severity at the provocation site at Week 12 and Week 24 using the peak pain sensation NRS (patient reported)
- Change from baseline in cold urticaria signs and symptoms severity at Week 24 on cold exposure days as measured by ColdUAS
- Change from baseline in health-related quality of life (HRQoL) as measured by Dermatology Life Quality Index (DLQI) in participants ≥ 16 years old, and in Children's Dermatology Life Quality Index (CDLQI) in participants ≥ 12 to < 16 years old at Week 24
- Change from baseline in Cold Urticaria Quality of Life (ColdU-QoL) at Week 24

The Week 12 and Week 24 values will be analyzed separately and use the same procedure as the key secondary endpoint. The endpoint change from baseline in DLQI will be summarized and analyzed in participants ≥ 16 years old who completed the DLQI at baseline. The endpoint change from baseline in CDLQI will be summarized separately in participants ≥ 12 to < 16 years old using descriptive analysis only.

The proportion endpoints below will be analyzed like the primary endpoint.

- Proportion of well-controlled participants (UCT ≥ 12) at Week 24
- Proportion of participants with an improvement of ≥ 3 in UCT 4-item from baseline to Week 24
- Proportion of participants with negative ice cube provocation test at Week 12

The two endpoints below will be summarized using the count and percentage of participants.

[figure not shown]
- Proportion of participants receiving rescue therapy for primary acquired chronic induced ColdU during the planned treatment period
- Proportion of participants with cold exposure triggered urticaria requiring emergency medical care visit or treatment with epinephrine (at provocation test and/or at home)

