4.6 MULTIPLICITY ISSUES

To strongly control the family-wise type-I error rate for testing the primary and selected secondary endpoints, hierarchical testing procedure is used. The overall two-sided alpha is 0.01. The comparisons with placebo will be tested based on the hierarchical order below at 2-sided $\alpha = 0.01$.

Order of the testing hierarchy:

1. Proportion of participants with negative ice cube provocation test at Week 24.
2. Change from baseline in local wheal intensity at the provocation site at Week 24 using the wheal intensity Likert scale ranging from 0 to 5 (clinician evaluation).
3. Change from baseline in proportion of cold urticaria symptom free days at Week 24 (exposure-adjusted and measured by ColdUAS).
4. Change from baseline in local itch severity at the provocation site at Week 24 using the Peak Pruritus Numerical Rating Scale (NRS, score 0 to 10) (patient reported).
5. Change from baseline in health-related quality-of-life (HRQoL) as measured by Dermatology Life Quality Index (DLQI) in participants ≥ 16 years old.

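### Disease control is the only secondary objective worded as something to demonstrate that has no endpoint in the SAP 4.6 testing sequence; adding UCT change as a last step would close the gap at no cost in alpha or in power for steps 1 to 5.

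*SAP*

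**What the plan says.** Protocol Tables 1 and 2 and SAP Table 1 list the secondary objectives in the same order. The first is "To demonstrate the efficacy of dupilumab on primary acquired chronic inducible ColdU disease control". Its only endpoints are three UCT measures at Week 24, which SAP 4.4.2 lists among the supportive secondary endpoints:

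- "Change from baseline in urticaria control test (UCT 4-item) at Week 24"
- "Proportion of well-controlled participants", meaning UCT of at least 12
- "Proportion of participants with an improvement of" at least 3 points on the UCT

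Protocol 3.1 says that "it is important to assess disease control over the course of treatment" in addition to symptoms, and describes the UCT as validated. Protocol 8.1.4 gives its minimal important difference (MID) as 3.

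On multiplicity, SAP 4.6 says: "To strongly control the family-wise type-I error rate for testing the primary and selected secondary endpoints, hierarchical testing procedure is used". The overall level is two-sided 0.01. The order is negative ice cube test, wheal intensity, ColdUAS symptom-free days on exposure days, peak pruritus NRS, DLQI. Protocol 9.4.1 promises error control for the primary endpoint, a selection of patient-reported outcomes and the other key secondary endpoints, and leaves the details to the SAP.

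SAP 4.4.2 analyses UCT change by the key-secondary ANCOVA, which reports p-values, and the two UCT proportions by the primary-endpoint method. Neither document calls these p-values nominal.

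**The concern.** The objectives tables choose their verbs with some care. Four secondary objectives are to be demonstrated. Rescue therapy, cold-triggered urticaria, safety and immunogenicity are to be evaluated. A reader would expect each objective in the first group to have at least one endpoint tested under error control. Three do, and disease control does not, although it is listed first.

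Two things are at stake. If dupilumab improves control, the trial cannot say so with a controlled error rate, however well steps 1 to 5 go. And three correlated p-values will be reported for one objective with no rule for reading them.

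**Working it through.** **1. Objectives against the sequence.**

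| Secondary objective to be demonstrated | Endpoint in SAP 4.6 |
|---|---|
| Disease control (UCT, three endpoints) | none |
| Local signs and symptoms after provocation | wheal intensity (step 2), itch (step 4) |
| Disease activity (ColdUAS) | symptom-free days (step 3) |
| Quality of life, disease status and severity | DLQI (step 5) |

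Steps 4 and 5 (itch and DLQI at Week 24) also appear in the supportive list of SAP 4.4.2. So being listed as supportive does not by itself keep an endpoint out of the sequence.

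**2. The plan's own figure, family-wise alpha 0.01.** In a fixed sequence, let step k be the first true null in the order. No false rejection is possible unless step k is rejected, which happens with probability at most 0.01. Hence the family-wise error is at most 0.01 for five steps. The argument does not depend on the number of steps, so it holds for six. Simulation of 1,000,000 trials per setting, with the first true null at each position and correlations 0, 0.3, 0.5 and 0.8, gave 0.0098 to 0.0102 for six steps.

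**3. Effect on steps 1 to 5.** Step 6 is read only after step 5 has been rejected, and it passes nothing back. The rejection probabilities of steps 1 to 5 are therefore identical with and without it.

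**4. The three UCT p-values under no effect.** If independent, the chance that at least one is below 0.01 is 1 − 0.99³ = 0.0297. They are correlated, so the true figure is a little lower. Assumptions, none of which is in the documents: scores rounded and limited to 0–16, baseline mean 6 and SD 3, Week 24 mean 9 and SD 4, correlation 0.5, unstratified tests for the two proportions. Result: about 2.6%. Repeat runs over SD 3 to 5 and 35 or 39 per arm gave 2.3% to 2.7%.

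**5. Marginal power of UCT change at 0.01 for a 3-point difference.** The sample size is 39 per arm. With 10% drop-out, 39 × 0.9 ≈ 35. The normal approximation is power = Φ(δ/SE − 2.576), with SE = SD × √(1 − r²) × √(2/n). For SD 4, r = 0.5, n = 35: SE = 4 × 0.866 × 0.239 = 0.828; 3/0.828 = 3.62; Φ(3.62 − 2.576) = Φ(1.05) ≈ 0.85. Simulation gives less, mainly because the ceiling at 16 shrinks the observed difference to about 2.7 points:

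| UCT SD (assumed) | Simulated power, 35–39 evaluable per arm |
|---|---|
| 3 | about 97–99% |
| 4 | about 82–85% |
| 5 | about 54–61% |

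A repeat run agreed to within about two percentage points.

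**6. Overall chance of a controlled UCT claim.** All five earlier steps must pass first. If each has 90% marginal power and they are independent, 0.9⁵ = 0.590. With UCT at SD 4, 0.590 × 0.82 = 0.48 to 0.590 × 0.85 = 0.50. If all six have 90% power, the chance is 0.9⁶ = 0.53, and 0.62, 0.68 and 0.78 for correlations of 0.3, 0.5 and 0.8. If all six have 80%, it is 0.26, 0.40, 0.48 and 0.62. Under the SAP as written it is zero.

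**The case against.** The strongest reply is that the plan is consistent with itself. The protocol promises error control only for the primary endpoint, selected patient-reported outcomes and key secondaries. ColdUAS, itch and DLQI satisfy that, and the choice belongs to the sponsor. UCT is listed as supportive, and study success rests on the primary endpoint alone. This stands: a reader might infer a breach of the multiplicity text, and there is none. The mismatch is between an objective's wording and the status of its endpoints. Changing the verb to *evaluate* would also remove it, but would give up the claim.

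Three other stronger readings also fail.

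- *An error rate of about 12% against a promised 1%.* That figure counts any UCT p-value below 0.05. The 1% applies only to the sequence, and no passage says UCT will be judged at 0.05. At 0.01 the figure is about 2.6%, for endpoints outside the protected family.
- *About 86% power to show disease control.* That is conditional on steps 1 to 5, assumes 39 evaluable per arm and rests on one assumed SD. Working steps 5 and 6 give the fuller range.
- *UCT of at least 12 could follow as step 7.* Criterion I 04 requires only one of three conditions, so a participant may enter on a recent history of anaphylaxis, oropharyngeal edema or emergency care with UCT already at 12 or more. Such a participant could count as well controlled at Week 24 without improving.

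The objective "To demonstrate improvement in health-related quality-of-life and overall disease status and severity" still names disease status and severity after PGIC and PGIS became exploratory. That is an editorial remnant and adds nothing to this point.

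**Conclusion.** The point holds as an avoidable gap, not as an error in the trial's inference. The primary analysis and the 0.01 family-wise guarantee for the five listed steps are sound. What is missing is any route to an error-controlled statement on disease control, the only one of the four objectives to be demonstrated that is left without one.

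The zero cost of a sixth step follows from the structure of a fixed sequence and needs no assumption about UCT. It holds only for the last position: placed earlier, UCT would put the steps after it at risk. The size of the gain does rest on assumptions, since the documents give no UCT SD, baseline mean, correlation or expected effect. At the stated MID, marginal power runs from just over one half to nearly certain over SD 5 to 3.

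**What to change.** Before database lock and unblinding:

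1. In SAP 4.6, add a sixth step, "Change from baseline in urticaria control test (UCT 4-item) at Week 24", tested at two-sided 0.01 only if steps 1 to 5 are all significant.
2. State in SAP 4.6 that p-values for endpoints outside the sequence, including the two UCT proportions, are nominal.
3. Do not make UCT of at least 12 a confirmatory step unless the SAP first says how participants with a baseline UCT of 12 or more are handled.

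The cost is two sentences of SAP text. No further participants or assessments are needed, because UCT is already collected and analysed. The protocol leaves the detailed procedure to the SAP, so its multiplicity text need not change.
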